### *Missing values*

Missing values will not be imputed. An advantage of LME models is that they can automatically tolerate missing values by adjusting the respective covariance estimates. Moreover, missing data for the primary outcome is expected to be minimal as this BP data will be collected at the study visits by the investigators.

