## 2.6 Statistical Methods

### 2.6.1 Determination of Sample size

In a previous study of daily BRJ (400mg nitrate) supplementation in hypertensive patients (n=68) for 4 weeks, systolic BP was significantly reduced by 7.7mmHg (3.6-11.8 mmHg,  $p<0.001$ ) at the end of the intervention. The average BP of the two groups were 148 mmHg and 149 mmHg, with standard deviations of the two populations being 10 and 11.[1] We expected to have a similar hypertensive population and to detect this difference in systolic BP with an  $\alpha=0.05$  and power of 0.80, 28 participants are required in the each treatment group. To account for drop-out, the sample size was increased to 30 participants per treatment group (total n=60).

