### 2.6.2 Statistical and Analytical Plans

#### *Primary Endpoint Analysis*

The co-primary endpoints are the change in mean of second and third systolic and diastolic BP measurements taken at Visit 1 (pre-intervention) and at Visit 3 (at the end of week 4 of the intervention). Initially, sample mean and standard deviation will be reported at baseline and follow up. Moreover, their mean difference and standard deviation will be reported. Secondly, the main analysis will be conducted using a Gaussian linear mixed effects (LME) model with a first-order autoregressive correlation structure (AR(1)). The repeated measures are the BP results at Visit 1 and Visit 3. An interaction parameter between Visit and Arm of study will be the determinant of a significant difference in BP change between the two arms. The model will be adjusted for the following prognostic factors: age, eGFR and baseline serum nitrate/nitrite levels. The sensitivity analysis will only be adjusted for age and eGFR. Should any variables differ significantly between the two arms, they too will be adjusted for to eliminate the possibility of a confounding effect. No subgroup analyses will be undertaken. All data analysis will be completed in R version 3.6.2 (R Core Team). All (potential) confounding variables will be summarised using t-tests or rank sum tests for continuous variables and chi-squared tests or Fisher's exact tests for categorical variables. Means (standard deviations) and counts (column percentages) as well as relevant p-values will be reported. Hypotheses will be conducted with a two-sided alternative and p-values less than 0.05 will be considered statistically significant.

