## **2.12.2 Sampling procedures**

**Blood:** At visit 1 and 3, after five minutes of rest (as plasma nitrate levels are affected by rapid changes in posture [52]), venous blood will be collected by venepuncture into one 8mL SST tube, which will immediately be centrifuged at 1000 x g (15 min at 4 °C) to separate the serum. The serum will be stored in aliquots and frozen at -30 °C until measurement. Serum samples will be used for measurement of NO metabolites (nitrate and nitrite) using a nitric oxide assay and asymmetric dimethylarginine ADMA (a NOS inhibitor and recognized marker of endothelial dysfunction) using ELISA.

To determine if patients fit the inclusion criteria at visit 1 (ie. Serum creatinine, absence of diabetes and uncontrolled hyperlipidemia), patients can provide results of a recent blood test or will have routine bloods performed.

**Urine:** Two urine samples will be collected at Visit 1 and 3. After participants return their urine collection bottles, one sample will be weighed and stored at -30 °C for measurement of NO metabolites (nitrate/nitrite and *N*-nitroso compounds), and the other sample will be sent for formal urine albumin to creatinine ratio measurement. The sample to be stored for *N*-nitroso measurement will be aliquoted and preserved in sodium hydroxide based on previous research that this improves the preservation of volatile *N*-nitroso compounds if any are present.[53]

**Saliva:** Whole saliva samples will be collected from participants at Visit 1 and 3 for genomic analysis of oral bacteria. Participants will be asked to rinse their mouths with bottled water at least 10 minutes prior. A spit saliva sample will be collected in sterile tube. Samples will then be aliquoted into 1.5mL Eppendorf tubes and stored at -80 °C.

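### The no-imputation rule relies on a tolerance that mixed models have for missing outcomes, not for the missing baseline nitrate/nitrite covariate in the primary model

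*Combined protocol and SAP*

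**What the plan says.** Under Missing values, section 2.6.2 states "Missing values will not be imputed" and exempts no variable. The reason given is "An advantage of LME models is that they can automatically tolerate missing values by adjusting the respective covariance estimates". The only further reassurance is that little primary outcome data should be missing, because investigators measure BP at the visits. Covariates are not mentioned.

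Under Primary Endpoint Analysis, the main model is a Gaussian mixed model with AR(1) correlation on the Visit 1 and Visit 3 clinic BPs, and the Visit by Arm interaction decides the result. "The model will be adjusted for the following prognostic factors: age, eGFR and baseline serum nitrate/nitrite levels". A sensitivity analysis keeps age and eGFR only. Under Secondary Endpoint Analysis, the home BP model uses the same three covariates.

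Section 2.12.2 gives the source of the covariate: "venous blood will be collected by venepuncture into one 8mL SST tube", with the serum divided into aliquots, frozen, and later used for both the nitric oxide assay and ADMA.

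**The concern.** A likelihood-based mixed model can use a participant who has one BP reading and lacks the other. It cannot use a record whose fixed-effect covariate is missing, because the mean of that record is then undefined. Baseline nitrate/nitrite is a single value per participant, so one missing result removes both clinic BP records.

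The gap can arise under this design. Age and eGFR are tied to eligibility (Table 1 and section 2.4) and should be almost complete. Nitrate/nitrite is not an eligibility item and is measured from stored serum, so its absence may be found only after the participant has been randomised and followed up.

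At stake are precision and the definition of the primary analysis set. Randomised participants with complete primary outcome data could be left out of the main analysis but kept in the sensitivity analysis. With no stated rule, the handling would be chosen after the data are in.

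**Working it through.** **Inputs.** From section 2.6.1: difference 7.7 mmHg ("systolic BP was significantly reduced by 7.7mmHg"), SDs of 10 and 11 (mean 10.5), and "power of 0.80, 28 participants are required in the each treatment group", raised to 30 per group for drop-out. From section 2.6.2: "Hypotheses will be conducted with a two-sided alternative" at the 0.05 level. The rate of missing baseline nitrate/nitrite is not in the documents; 5% to 20% is assumed, split equally between arms.

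**1. The plan's own figure.** By the normal formula, n per arm = 2 × (1.960 + 0.842)² × SD² / 7.7².
- SD 10: 2 × 7.849 × 100 / 59.29 = 26.5, so 27. The exact t-test needs 28.
- SD 10.5: 29.2, so 30. The exact t-test needs 31.
- SD 11: 32.0, so 33. The exact t-test needs 34.

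The stated 28 is reproduced with SD 10. The drop-out allowance is 2 × (30 − 28) = 4 people in total.

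**2. What the model does with each kind of gap.** I fitted the planned mean structure to one simulated data set with 60 participants and two visits (true effect −7.7, between-person SD 8, residual SD 7, all illustrative). A random participant intercept stood in for AR(1); with two visits, either structure has a single correlation.

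| Situation | Rows used | Participants | Visit × Arm (SE) |
|---|---|---|---|
| Complete data, with nitrate/nitrite | 120 | 60 | −8.042 (2.373) |
| Complete data, age and eGFR only | 120 | 60 | −8.042 (2.373) |
| 6 Visit 3 BPs missing | 114 | 60 | −9.109 (2.637) |
| 6 baseline nitrate/nitrite values missing | 108 | 54 | −7.712 (2.602) |
| Same 6, filled with overall mean | 120 | 60 | −8.042 (2.373) |

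R's nlme functions behave in the same way. By default they stop with a missing-values error; when told to omit incomplete rows they keep 108 rows and 54 participants. This was run in R 4.3.3; the plan names 3.6.2.

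The third row is the case that the plan's statement covers. The fourth is the case that it does not.

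**3. Why the fill returns the complete-data result.** With both BPs present, the Visit × Arm parameter is the difference between arms in mean (Visit 3 − Visit 1). A covariate that is constant over time and enters only as a main effect cancels in that within-person difference. It therefore changes neither the estimate nor its SE, and the value filled in does not matter. Deleting 6 of 60 does matter: the SE is expected to grow by about √(60/54) = 1.054, and a single data set will scatter around that.

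**4. Power.** Two-sided t-test with noncentrality 7.7 / (SD × √(2/n)). For SD 10 and n = 30 this is 7.7 / (10 × 0.2582) = 2.98, giving 83.5%.

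| Lost from 60 | n per arm | SD 10 | SD 10.5 | SD 11 |
|---|---|---|---|---|
| 0 | 30 | 83.5% | 79.8% | 76.0% |
| 3 (5%) | 28.5 | 81.5% | 77.6% | 73.8% |
| 4 (6.7%) | 28 | 80.8% | 76.9% | 73.0% |
| 6 (10%) | 27 | 79.3% | 75.3% | 71.4% |
| 12 (20%) | 24 | 74.3% | 70.1% | 66.1% |

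Four losses of this kind use up the whole drop-out allowance before anyone has dropped out. These figures follow the plan's two-sample comparison, not the mixed model.

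**The case against.** The strongest reply is that little is lost. The age and eGFR model is already pre-specified and keeps these participants, so they do not vanish from the trial's analyses. That stands. It does not repair the main analysis, which carries the conclusion; nor is the sensitivity model offered as a remedy for missing data.

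A reader might infer that the deletions would bias the comparison. The documents do not support this. The sample is taken at Visit 1, before any juice is drunk, and staff in contact with participants are blinded. Nothing suggests that a missing pre-dose result would depend on arm.

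A reader might also infer that a gap between the main and sensitivity results would mix a covariate effect with a change of participants. With complete BP data it would not, because the covariate does not act on the deciding parameter (step 3). The gap would reflect the change of participants alone.

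The frequency is unknown. A single tube does not mean a single chance at the assay, since the serum is aliquoted and a failed run may be repeatable. The loss need not be silent either, as the default in R is an error. The defect is a wrong justification and an unstated handling step.

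Finally, falling below 80% power cannot be put down to missing assays alone. With SD 10.5, power is already 79.8% with nobody lost.

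**Conclusion.** The Missing values text is wrong as written: the tolerance it claims does not extend to covariates, and the main and home BP models contain a covariate that can be missing. The consequence is lost precision and a primary analysis set that may be smaller than the sensitivity set. Bias by arm is not shown.

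At an assumed 10% missing, the cost is 4.2 to 4.6 percentage points of power across SDs of 10 to 11. At a low failure rate it is small. The conclusion about the mechanism needs no assumed rate; the size depends on the assumed rate, on equal loss in both arms and on the two-sample formula. Because the covariate adds nothing to the Visit by Arm estimate when both BPs are present, keeping everyone in the model carries no penalty on the deciding parameter.

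**What to change.** In section 2.6.2, Missing values, replace the general rule with wording such as:

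> Missing outcomes are not imputed. A missing baseline nitrate/nitrite value is replaced by the overall baseline mean computed without regard to arm, so that every randomised participant with clinic BP data is included in the primary model. The primary and sensitivity models are fitted to the same participants.

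The filled value should serve only as a covariate, there and in the home BP model, and never as an observation of the nitrate/nitrite endpoint. The Summary repeats the models but contains no missing-data rule, so it needs no change.

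Other workable choices are multiple imputation of the covariate, or making the age and eGFR model primary. The mean fill is the smallest change. It costs about two sentences and one line of code, needs no new data, and its downside is one simple single imputation of a baseline covariate. It should be fixed before unblinding.

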## **2.7 Study Intervention**

### **2.7.1. Method of Administration**

Participants will self-administer the intervention at the same time. The intervention will be an oral dose of nitrate-rich BRJ (70mL Beet-IT SportTM; James White Drinks, UK; 400mg nitrate/70mL) taken once daily while the placebo is an identically packaged nitrate-depleted beetroot juice (identical drink and volume with nitrate content removed). The trial team will document the expected time of BRJ consumption at Visit 1 and confirm this at Visit 3.

### **2.7.2. Dose of BRJ**

A minimum dose of  $\geq 5\text{mmol}$  of  $\text{NO}_3^-$  per serving has been shown to be required to enhance exercise performance in most healthy individuals.[45] Beet-IT SportTM (James White Drinks) contains  $6.41 \pm 0.60\text{ mmol}$  of  $\text{NO}_3^-$ , or 400-500mg nitrate per serving.[46] Beetroot juice also contains other bioactive compounds that may provide minimal additive BP lowering effects such as vitamin C, magnesium, betaine and flavonoids.[47] Potentially confounding effects of other vasoactive components of beetroot juice will be limited by using the identical drink with depleted nitrate content (manufactured by James White Drinks). The nitrate-depleted placebo beetroot juice is identical in taste, appearance and packaging.

In previous studies, BRJ lowered blood pressure after at least 21 days of continuous supplementation. A significant reduction in home systolic blood pressure during the 3rd and 4th week of intake occurred after ingesting BRJ (6.41mmol  $\text{NO}_3^-$ , 400mg nitrate, 70 ml, James White Beet-IT Sport Shot) in older, overweight individuals with high-normal blood pressure.[48] No effect was observed in blood pressure measured by clinic or ambulatory blood pressure (AMBp), but a reduction in 7.3 mmHg was seen in home systolic blood pressure readings. This was potentially attributed to participants not being asked to record their physical activity during the 24-hour ABPM recording period, and lower nitrate concentration consumed than reported by manufacturer and differences in nitrate metabolism in older patients.[48] Drug naïve hypertensive patients demonstrated a reduction in clinic, home and ambulatory systolic blood pressure that persisted throughout the entire 4 weeks of daily a single dose of BRJ (250mL, 6 mmol  $\text{NO}_3^-$ , James White Beet-IT Beet Juice) in treated participants

on an unaltered diet.[20] The reduction in clinic BP was 7.7/2.4mmHg (3.6-11.8/0.0-4.9,  $p<0.001$  and  $p=0.050$ ).[20] The home blood pressure measurements over the 4 weeks demonstrated an increasing magnitude of the effects with time; comparable with a standard dose of antihypertensive medication, with a reversal occurring only on washout. However, in contrast, in 2015, Bondonno *et al.* showed no effect on home and clinic blood pressure after 1 week of treatment with BRJ (2 x 70mL, 600mg nitrate; James White Beet-IT Shot) in individuals with high-normal blood pressure and treated hypertensives, despite parallel increased nitrate metabolism. This could be due to the relatively short duration of supplementation, and potential interference of multiple anti-hypertensive pharmacologic agents (2-3 per individual), low-nitrate diet, and/or extended time period between each dose.[49] Finally, in 2013, Gilchrist *et al.* observed no effect on blood pressure, macro or microvascular endothelial function after 2 weeks of BRJ (250mL, 450mg nitrate; James White Beet-IT) in hypertensive individuals with Type 2 diabetes mellitus. This was also potentially attributed to the relatively short duration of intervention, and the numerous biochemical perturbations associated with diabetes which leads to diminished vascular reactivity and impaired responsiveness NO.[33] Therefore for reproducibility and comparability, the current study will administer “Beet-IT Sport Shot” (70mL; James White Drinks, UK) containing ~400mg nitrate per dose for a duration of 4 weeks.[46]

#### 2.7.3. Source of BRJ

BRJ will be purchased from James Whites Drinks (United Kingdom) as it is the brand most commonly used in previous trials. The manufacturer also provides a standardised placebo where the taste and appearance are identical to the nitrate-replete BRJ. The content of the placebo is identical to the active compound but has nitrate extracted is shown in Table 2.

**Table 2:** Product specifications of the BRJ (nitrate replete and nitrate depleted) according to manufacturer

| Parameter     | BEET-IT SPORT SHOT            | BEET-IT PLACEBO |
|---------------|-------------------------------|-----------------|
| Volume        | Per 70 ml                     | per 70 ml       |
| Nitrate       | 0.4 g                         | 0               |
| Energy        | 305 kJ                        | 305 kJ          |
| Carbohydrates | 15.4 g (of which 14.g sugars) | 15.4 g          |
| Protein       | 2.5 g                         | 2.5 g           |
| Salt          | 0.2 g                         | 0.2 g           |

#### 2.7.4. Management of BRJ

The product will be stored in batches at room temperature (according to recruitment rate), according to the manufacturer’s specifications, in a storage room. BEET-IT is a natural product containing beetroot juice (BRJ) that is available over the counter and freely available for purchase by the community. Based on the TGA’s Food-Medicine Interface Guidance Tool <https://www.tga.gov.au/community-qa/food-and-medicine-regulation> BEET-IT is classified as a ‘food’ and not a ‘medicine’ (drug) (Table 3). Therefore, the oversight, dispensing and recording of BEET-IT consumption will be undertaken by study staff without involvement of pharmacy.

Accountability, shipping record (shipment dates, batch numbers and method of shipment), storage conditions (location, temperature, amount of ambient light) of the investigational product (nitrate-replete and -depleted BRJ) will be maintained in data logs according to ICH-GCP guidelines and will be the responsibility of an Associate Investigator (AI). This AI will be unblinded to the product (nitrate-rich vs nitrate-depleted) for appropriate storage, labelling and management of the product to ensure participant-facing investigators remain blinded. Nitrate-rich and nitrate-depleted BRJ will have identical packaging however the AI will be in independent contact with the manufacturer and be aware of which batch numbers correlate with nitrate-rich and nitrate-depleted BRJ, without the other investigators aware of which BRJ batch is being allocated, and so that investigators with participant contact can disseminate the product without unblinding themselves.

**Table 3:** Food-Medicine Interface Guidance Tool applied to BEET-IT

|            | Food-Medicine Interface Guidance Tool Question   | BEET-IT |
|------------|--|---------|
| 1          | Is the product for oral use for humans?  | Yes     |
| 2          | Is there a (post 2010) s.7 declaration in relation to the product that it is a therapeutic good?   | No      |
| 3          | Is the product covered by a s.7AA declaration?   | No      |
| 4          | Is the product 'goods' for which there is a standard in the Food Standards Code?   | No      |
| 5          | Is the product goods which, in Australia or NZ, have a tradition of use as foods for humans in the form in which the thing is presented?                                       | Yes     |
| Conclusion | The product is not a 'therapeutic good'. It is likely to be 'food' within state/territory food regulation legislation and/or regulated under other state/territory legislation |         |

## 2.8 Randomisation and Blinding

### 2.8.1 Blinding

Blinding and storage will be undertaken as per Management of Investigational Product by an AI who is not participant facing and does not conduct study procedures. All other investigators and research staff will be blinded to the treatment allocation. Nitrate-rich and placebo BRJ will be identical in appearance and taste with a batch number allocated to each participant. Treatment assignment in the groups will be blinded to participants and all other investigators until data lock and statistical analysis.

Both participants and outcome assessors will be blinded to participants' treatment allocations, to reduce the risk of bias in the study. Awareness of the intervention assigned to participants can introduce ascertainment bias in the measure of outcomes; particularly subject ones, performance bias in the decision to discontinue or modify study interventions (e.g. with dosing changes of beetroot juice), concomitant interventions, and exclusion bias in the decision to withdraw from the trial or exclude a participant from the analysis.

Emergency unblinding procedures, namely, revealing the assigned intervention to participants and investigators, will only occur in certain circumstances with the intention to increase the safety of trial participants, should any evidence of harms or other relevant conditions arise. However, in some cases (i.e. minor, reversible harms), stopping and then cautiously re-introducing the assigned intervention in the affected participant can avoid both unblinding or causing further harm.

#### **2.8.2 Randomisation**

Eligible participants will be randomised 1:1 at Visit 1 to receive either dietary nitrate or placebo using a simple randomisation program created by the study biostatistician, which uses a random number generator (version 3.6.2, R Core Team). This program creates a list that allocates treatment or placebo (1:1) to 60 unique study IDs. No stratification factors will be used. Participants will not consume the intervention until instructed to by trial staff at Visit 2.

If a participant is deemed ineligible between Visit 1 and 2, they will be asked to return the sealed beetroot juice given to them to the trial staff. The AI who is responsible for blinding will reallocate the BRJ as per the randomised number list created by the statistician.

#### **2.8.4 Contamination**

Bias and contamination could be introduced by a participant's expectations and prior knowledge of the hypothesised benefits of inorganic nitrates in ADPKD. To mitigate this, both groups will be educated on that fact that these benefits have not been proven in human studies in ADPKD; the consent form will be written in an objective, neutral manner to accurately reflect current evidence.

### **2.9 Concomitant care**

Participants will be requested to avoid the use of mouthwash from Visit 1 until study completion as the blood pressure lowering effects of dietary nitrate have been reported to be abolished by the use of antiseptic mouthwash due to the removal of normal oral commensal bacteria.[50]. Participants will be advised to continue their usual medications, diet, physical activity, and other lifestyle factors as directed by their treating nephrologist. As described above (section 2.1), participants must be on a stable blood pressure regime for 28 days at the time of screening. All participant medications, supplements and procedures will be recorded at screening and prompted for at each study visit. If a participant requires a change in blood pressure medication as indicated by their own doctor during the study, they will be withdrawn from the study. Where a participant requires antibiotics in the month prior to commencing the study, or during the study period, it will be recorded as its impact on the oral microbiome ability to covert BRJ to NO is not known.

